BP	Blood Pressure				
CRF					
	Case Report Form Chronic Rhinosinusitis				
CRS					
DLT	Dose Limiting Toxicity				
DSMB	Data and Safety Monitoring Board				
EKG	Electrocardiogram				
ELISA	Enzyme Linked Immunosorbent Assay				
FDA	Food and Drug Administration				
GAPDH	Glyceraldehyde-3-Phosphate Dehydrogenase				
GCP	Good Clinical Practice				
HCl	Hydrochloride				
IHC	Immunohistochemistry				
IL	Interleukin				
IN	Intranasal				
IND	Investigational New Drug				
IRB	Institutional Review Board				
ICC	Intraclass Correlation Coefficient				
IŢ	Intermediate Toxicity				
LMK	Lund-Mackay				
LKS	Lund-Kennedy Score				
LSM	Least Squares Mean				
MAD	Maximal Administered Dose				
MAP	Mean Arterial Pressure				
MCID	Minimally Clinically Important Difference				
MEEI	Massachusetts Eye and Ear Infirmary				
MTD	Maximal Tolerated Dose				
PBS	Phosphate Buffered Saline				
PCFD	Partition Coefficient of the Free Drug				
P-gp	P-glycoprotein P-glycoprotein				
PI	Principle Investigator				
PVA	Polyvinyl Alcohol Sponge				
SA	Specific Aims				
SNOT-22	Sinonasal Outcomes Test (22-item)				
sNP	Without Nasal Polyps				
SEB	Staphylococcal aureus enterotoxin B				
TEM	Transmission Electron Microscopy				
Th2	Type 2 Helper T-cell				
TID	Three Times a Day				
TSLP	Thymic Stromal Lymphoprotein				
UCF	Ultracentrifugation				
wNP	With Nasal Polyps				
VAS	Visual Analog Scale				
	ž				
Zos	Zosuquidar Trihydrochloride				

STATEMENT OF COMPLIANCE

This trial will be conducted in accordance with the ICH E6, the Code of Federal Regulations on the Protection of Human Subjects (45 CFR Part 46), and the <NIH IC> Terms of Award. The Principal Investigator will assure that no deviation from, or changes to the protocol will take place without prior agreement from the sponsor and documented approval from the Institutional Review Board (IRB), except where necessary to eliminate an immediate hazard(s) to the trial participants. All personnel involved in the conduct of this study have completed Human Subjects Protection Training.

I agree to ensure that all staff members involved in the conduct of this study are informed about their obligations in meeting the above commitments.

Principal Investigator: _		
	Print/Type Name	
Signed:		_ Date:

PROTOCOL SUMMARY

Title: Phase Ib/II Clinical Trial of Topical Verapamil HCl for Chronic Rhinosinusitis with Nasal

Précis: Phase Ib will be an accelerated titration, intrapatient dose escalation cohort, with double-

> dose step design. Participants will administer each dose Verapamil HCl dose intranasally BID. Weekly visits will occur for side-effect and escalation evaluations. Phase II will be an open label trial of 20 participants. The MTD determined in Phase Ib will be administered BID for 4 weeks.

Participants will be seen at baseline, 1 week, and 4 week for efficacy and side-effect

evaluations.

Objectives: Primary Objectives:

> -Perform a Phase IB trial of topical intranasal Verapamil HCl BID to determine the Maximal Tolerated Dose(MTD) using an accelerated titration design with intra-patient dose escalation. -Perform a Phase II trial of topical intranasal Verapamil HCl BID based on the Phase I MTD to determine safety and efficacy using both subjective and objective outcome measures of CRS. Secondary Objective:

-Determine whether mucus derived exosomal P-gp can be used as a non-invasive biomarker of CRS by correlating it with baseline symptoms of CRSwNP and treatment response to topical

Verapamil HCl at the MTD. **Endpoint**

Primary Endpoints:

Phase Ib: Defining the Maximal Tolerated Dose(MTD) of topical Verapamil HCl. DLT will be defined as a development of 2nd or 3rd degree heart block as measured by an EKG.

Phase II: determining the efficacy of topical Verapamil HCl at the MTD for subjective symptoms

of CRSwNP using the validated SNOT-22.

Secondary Endpoints:

Phase Ib: Intermediate toxicity will be defined as: a heart rate of <50, an asymptomatic BP reduction >30% from baseline or SBP <90mmHg, an asymptomatic AMP reduction >30% from baseline or MAP<55, an asymptomatic DBP reduction >30% from baseline, and a Meltzer Compliance Grade >4.

Phase II: to determine the efficacy of Verapamil HCl at the MTD as measured by a subjective 10cm visual analog scale(VAS), Meltzer topical irrigation satisfaction and compliance scores, and the validated Lund-Kennedy nasal endoscopy score(LKS).

Population: 20-40 MEE Sinus Center patients over the age of 18 who present with chronic

rhinosinusitis with polyps.

Phase: IB/II
Number of 1

Sites enrolling participants:

Description Verapamil HCl 0.3mg-3.6mg final dose BID in buffered normal saline as a nasal

of Study irrigation.

Agent:

[figure not shown]
Study December 2016 – December 2018

Duration:

[figure not shown]
Participant 1 month

Duration:

SCHEMATIC OF STUDY DESIGN

Legend				
IC	Informed Consent			
IF	Intake Form			
PT	Pregnancy Test			
SNOT-22	Sino-Nasal Outcome Test			
VAS	Visual Analogue Scale			

2 INTRODUCTION: BACKGROUND INFORMATION AND SCIENTIFIC RATIONALE

2.1 BACKGROUND INFORMATION

P-glycoprotein is overexpressed in Th2 polarized endotypes of CRS and correlates with indices of disease severity. Previous studies by our group have demonstrated that P-gp is differentially overexpressed in the sinus mucosa of patients with CRSwNP relative to CRS without Nasal Polyp(CRSsNP) and control patients. This overexpression is specific to the sinus mucosa as the adjacent non-polypoid septum has similar expression levels across all patient groups [10]. We next focused on the CRSsNP population to determine whether P-gp expression correlated with clinical severity. We found that high P-gp expression patients with CRS had greater tissue eosinophilia and worse CT inflammatory scores than their low P-gp expression CRSsNP counterparts. These findings indicate that P-gp is overexpressed in CRSwNP and eosinophilic CRSsNP, both of which are associated with Th2 polarized inflammation.

P-gp overexpression in CRSwNP directly leads to Th2 cytokine hyper-secretion. Having demonstrated that P-gp is overexpressed in Th2 polarized forms of CRS(CRSwNP and eosinophilic CRSsNP), we next studied whether this overexpression is associated with increased secretion of cytokines which promote Th2 inflammatory pathways. We utilized an organotypic explant model to confirm that P-gp is overexpressed in CRSwNP relative to non-eosinophilic CRSsNP. Using this explant model we showed that P-gp directly promotes the secretion of both IL-5 and thymic stromal lymphopoietin (TSLP). Furthermore, the degree of secretion of these important Th2 polarizing cytokines was strongly and significantly correlated with P-gp expression within the same explant[45]. These results confirm previous in vitro findings by our group in polyp derived epithelial cell cultures[44]. Taken together, these results demonstrate that P-gp mediated cytokine hyper-secretion plays a critical role in the pathogenesis of Th2 polarized forms of CRS including CRSwNP.

Mucus derived exosomal P-gp is a non-invasive biomarker of CRSwNP. Our group recently reported on the presence of a secreted form of P-gp which could be detected in nasal mucus. While the presence of P-gp in mucus is physiologic, we showed that total P-gp concentrations above 250 pcg/µg of total protein are associated with CRSwNP as well as more severe subjective and objective findings of disease[13]. We subsequently discovered that this secretion was mediated by the release of exosomes which are differentially enriched with P-gp among patients with CRSwNP. In light of the importance of P-gp overexpression to the pathogenesis of CRSwNP, the development of a non-invasive test of expression which intrinsically resists degradation and can be correlated with disease severity would be extremely valuable.

Verapamil HCl is an effective P-gp inhibitory therapy for CRSwNP. However well tolerated oral doses are subtherapeutic in patients with elevated BMI. The significant contribution of P-gp to the pathogenesis of CRSwNP suggests that it may represent a novel druggable target. We therefore undertook a randomized, double-blind, placebo-controlled trial to test the efficacy of low dose oral Verapamil HCl, a known first generation P-gp inhibitor[14], for the treatment of CRSwNP[19]. While Verapamil is cardioactive, it is considered a first-line prophylactic drug for cluster headache and is well tolerated at 80mg three times a day(TID) by otherwise healthy patients[51]. Our findings demonstrated significant efficacy in both our primary and secondary endpoints with no significant side effects. However, a logistic regression analysis revealed two important relationships between baseline characteristics and efficacy. First, patients with elevated BMI had significantly lower improvements in SNOT-22(p=0.01). This is consistent with our use of a low dose of a relatively low potency inhibitor. The second is that patients with the highest total mucus P-gp levels experienced less benefit(p=0.01). This strongly suggests that the mechanism of Verapamil is acting through P-gp inhibition and that patients with greater expression may need higher concentrations to achieve adequate pump suppression. While Verapamil HCl has significant potential for the treatment of CRSwNP through P-gp inhibition, higher doses must be achieved to extend the effect to patients with elevated BMIs and the highest levels of P-gp expression. As increasing oral dosing could result in cardiac side effects, topical delivery represents a promising alternative. As exosome bound P-gp may be more stable and representative of disease state than total mucus P-gp concentration, exosomal P-gp demands further exploration as a novel biomarker of disease severity and drug response.

Pharmacokinetic comparison of oral versus topical Verapamil administration. The bioavailability factor of Verapamil HCl has been estimated at 29-47.8% intranasal(IN) and 20-35% orally[52][53]. Due to the stereoselective first-pass effect of oral Verapamil, the dextro/levo isomer ratio should be taken into account indicating that 2-3 times higher Verapamil concentrations are needed to obtain a similar effect after oral versus IN administration [54]. The ratio of the IN/oral bioavailability divided by the stereoselective effect suggests that an IN dose of 11.2-48.5mg of Verapamil would be equivalent to a single 80mg oral dose. To achieve the same exposure effect at steady state TID dosing, the equivalent BID IN dose would therefore be 16.8-72.75mg. The partition coefficient of the free drug(PCFD), the unbound fraction capable of diffusing into the mucosa, has been estimated to be between 2.0-8.0[55][56][57]. Based on the mucosal volumetric analysis by Sarangapani et al[58], the PCFD of Verapamil, and

our previous ¬in vitro data[48], the minimal peak IN dose required to achieve an adequate suppression of P-gp by Verapamil would be 0.03mg.

2.2 RATIONALE

Treatment of CRSwNP poses a significant challenge as the mechanisms responsible for initiating and maintaining Th2 inflammation are poorly understood. Consequently, the development of cost effective, targeted therapies, with limited off target toxicity remains a significant unmet need. This knowledge gap has also hindered the discovery and validation of novel biomarkers which could be used to predict disease endotype and prognosis. This proposal is based on several recent discoveries suggesting that P-glycoprotein(P-gp) functions as a key immunomodulator of Th2 cytokine secretion in CRSwNP. The P-gp hypothesis of CRSwNP has yielded both a novel druggable target as well as a possible non-invasive biomarker of disease severity and treatment response. The successful completion of this proposal therefore has the potential to significantly shift the way we diagnose and treat CRSwNP.

CRSwNP is a prevalent disease associated with major direct and indirect costs. Acute and Chronic Rhinosinusitis are estimated to affect up to 16% of the US population. They account for approximately 11 million or 1% of all office visits per year in the US and are the most common cause for antibiotic prescriptions in the community[20] [21]. CRS alone impacts more than 30 million Americans resulting in \$6.9 to \$9.9 billion in annual healthcare expenditures [22,23] and \$12.8 billion in productivity costs[24]. The subset of patients in Europe with CRSwNP has been estimated to be between 2 and 4.3% [25][26][27] and is thought to be similar in the US. This population remains one of the most challenging subgroups of CRS to manage effectively.

There is a significant lack of innovative therapeutic strategies in CRSwNP. This is due, in large part, to a lack of clear understanding of the pathways involved in the initiation and maintainance of the inflammation characteristic of the disease. While corticosteroids remain the best studied and most effective treatment[28][29][30][31], they are non-targeted and are therefore associated with significant off target effects. Even when applied topically, steroids may be absorbed systemically[2] and their efficacy has been questioned in several clinical trials[32][33]. Currently, the largest body of literature exploring the pathogenesis of CRSwNP has focused on Th2 polarizing inflammation as a key feature of the disease process[34][35]. This has catalyzed the exploration of monoclonal antibody therapies which target specific Th2 promoting cytokines in CRS with variable clinical success.

Biologic therapies have had mixed results and are associated with significant drawbacks. Two anti-Interleukin(IL)-5 agents Reslizumab[36] and Mepolizumab[37] have been studied in the context of CRSwNP. While improvement was demonstrated among certain objective signs of inflammation, patient symptoms scores failed to significantly improve. Dupilumab, a fully human monoclonal antibody to the IL-4 receptor α subunit that inhibits both IL-4 and IL-13 signaling has also recently been studied[38] [3]. The most recent study compared patients with

CRSwNP treated with placebo to Dupilumab for 16 weeks. This study demonstrated a significant improvement in SNOT-22 of –18.1 in the Dupilumab group however significant treatment related side effects were reported including a 47% rate of nasopharyngitis and 40% rate of injection site reactions. While the outcomes are promising, the need for weekly injections, significant side effects, high cost, and potential for loss of efficacy over time suggest that the development of alternative, cost effective, targeted non-steroidal therapeutic strategies are still needed to optimize treatment of CRSwNP.

There is an unmet need for the discovery and validation of non-invasive biomarkers of CRSwNP. As personalized treatment of CRS continues to advance, the development of biomarkers of disease and endotype will become critical. A recent study by Tomassen et al[39] provided a proof of concept that an unsupervised partition based cluster analysis of tissue derived cytokines and inflammatory proteins could yield discreet clusters which correlated well with phenotypic characteristics. Despite the promise of this technique, the biomarkers studied required tissue sampling which was invasive, introduced the possibility of inter-patient heterogeneity in tissue composition, and protein degradation during the sampling and storage process. Furthermore, the inevitable medical therapies leading up to the surgical event at which the sampling occurred were not accounted for in the analysis. Consequently, a novel method of biomarker sampling which can be performed non-invasively in the outpatient setting prior to the initiation of medical therapy is needed. Ideally these biomarkers would directly participate in, and thereby closely reflect, the underlying pathophysiology and would be intrinsically resistant to degradation.

Mucus derived exosomes represent an ideal potential biomarker reservoir. Exosomes are 30–150 nm vesicles surrounded by a lipid bilayer that are released from epithelial cells into nasal mucus[40][41] [42]. Biophysically, exosomes are equivalent to cytoplasm and carry integral membrane proteins, mRNA, and regulatory microRNA reflective of their cell of origin. Studies have demonstrated that exosomes are able to shuttle their cargo to adjacent cells where they can exert a paracrine regulatory function on the recipient cell[43]. The tightly regulated composition of exosomes, their presence in nasal mucus, and their protective lipid bilayer make them a potentially ideal source of biomarkers for outpatient sampling which could out-perform total dissolved protein levels given their vulnerability to proteolytic degradation.

The discovery of a new pathogenic mechanism for CRSwNP which yields both novel targeted therapeutics and non-invasive biomarkers of disease would represent an important and significant advance in the field of Rhinology.

2.3 POTENTIAL RISKS AND BENEFITS

2.3.1 KNOWN POTENTIAL RISKS

Verapamil HCl is a cardioactive drug and thus there is a theoretical risk of cardiac side effects from the medication. This will be mitigated by obtaining a EKG which will be reviewed by a medical internist/anesthesiologist prior to initiating therapy. Follow-up EKGs will also be performed to monitor for cardiac side effects. The risk of cardiac effects appears to be dose-dependant and is expected to be mostly reversible upon discontinuation of the drug. Additional risks include bradycardia and hypotension. These will be mitigated by checking routine vital signs at each visit which will include heart rate and blood pressure. Constipation is also a risk of the drug. This will be asked about at each visit and stool softeners and/or laxatives will be administered as necessary. Since verapamil will be administered with a nasal rinse there is a possibility of nasal irritation. These side effects will be monitored at each study visit.

There are currently few medical interventions available for CRSwNP. The development of new medications is critical to the management of this disease. Thus, the short-term risks for the trial patients will ultimately decrease the risks and discomforts that the overall CRSwNP population experiences.

2.3.2 KNOWN POTENTIAL BENEFITS

If successful, using Topical Verapamil will help treat pateints with CRSwNP and potentially enable them to avoid sinus surgery or steroid therapy with their attendant risks.

Successful performance of Topical Verapamil will establish this drug as a novel therapeutic option for the treatment of CRSwNP as well as elucidate a mechanism of the pathophysiology of CRSwNP. This may also open avenues for the use of a new class of treatments for CRSwNP which work along the same mechanism.

3 OBJECTIVES AND PURPOSE

Primary Objectives:

- Perform a Phase IB trial of topical intranasal Verapamil HCl BID to determine the Maximal Tolerated Dose(MTD) using an accelerated titration design with intra-patient dose escalation.
- Perform a Phase II trial of topical intranasal Verapamil HCl BID based on the MTD to determine safety and efficacy using both subjective and objective outcome measures of CRS.

Secondary Objective:

- Determine whether mucus derived exosomal P-gp can be used as a non-invasive biomarker of CRS by correlating it with baseline symptoms of CRSwNP and treatment response to topical Verapamil HCl at the MTD.

4 STUDY DESIGN AND ENDPOINTS

4.1 DESCRIPTION OF THE STUDY DESIGN

ARM 1: Phase 1B

The phase IB study will consist of an accelerated titration, intrapatient dose escalation cohort, with double-dose step design. The initial single patient cohort will begin by taking 0.3mg (10mg of Verapamil in 240mL of buffered normal saline yielding an established 3% residual nasal dose) as a nasal irrigation BID for 1 week. The first dose f

each escalation will be administered in a 10th or 11th floor MEE clinic withhemodynamic monitoring. A medically trained member of the study staff with monitor the patient for one hour. Patients will be instructed on the how to properly perform the irrigation using a pre-recorded video demonstration. If no first-course dose limiting toxicity (DLT, defined by the development of 2nd or 3rd degree heart block) is noted then patients will continue taking the current Verapamil rinse dose BID for 1 week. Dose escalation will occur weekly in the absence of a single, any course, DLT or a second, any course, intermediate toxicity(IT, defined by a heart rate of <50, an asymptomatic BP reduction >30% from baseline or systolic BP <90mmHg, an asymptomatic MAP reduction >30% from baseline or MAP<55, an asymptomatic diastolic BP reduction >30% from baseline, and a Meltzer Compliance Grade >4[60]). Each escalation will be a doubling of the dose from 0.3-2.4mg. At that point that dose will escalate in 0.6mg residual intervals for the rest of the trial up to a maximum of 3.6mg total residual dose. These doses were derived from the pharmacokinetic analysis of our oral Verapamil trial results. If a single, any course, DLT or second, any course, IT occurs, two additional patients will be recruited at that identified dose and Phase IB will revert to a standard 3+3 design. If any patient un-enrolls while the dose escalation is still occurring, they will be replaced to maintain 3 patient cohorts. The maximal administered dose(MAD) will be considered that at which at least 2 DLTs or 4 ITs occur and the MTD will then be assigned to the immediate preceeding dose.

At each weekly visit, the patients nasal endoscopy will be recorded for LKS grading, and they will be administered symptom, side-effect, and tolerability questionnaires. Pre-dosing mucus and post-dosing irrigant samples will also be atraumatically collected from the nasal cavity for use in exosomal biomarker sampling.

ARM 2: Phase 2

The Phase II study will be an open label safety and efficacy expansion cohort using the MTD determined in the Phase IB arm. A total of 20 patients will be administered the MTD of topical Verapamil HCl in a 240mL buffered normal nasal rinse for 4 weeks BID. This sample size was calculated based on a power analysis derived from the results of our oral Verapamil trial. The first dose will be administered in in a 10th or 11th floor MEE clinic withhemodynamic monitoring. A medically trained member of the study staff with monitor the patient for one hour. Patients will be instructed on the how to properly perform the irrigation using a pre-recorded video demonstration. If no first-course DLT occurs then patients will continue taking the topical Verapamil dose BID. Patients will then return for follow-up visits at 1 week and 4 weeks. Subjective and objective outcome measures will be collected at each visit.

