4.2.1 PRIMARY ENDPOINT

Phase Ib:

The primary outcome measurement for Phase IB(SA1) will be defining the Maximal Tolerated Dose(MTD) of topical Verapamil HCl. Dose Limiting Toxicity will be defined as a development of 2nd or 3rd degree heart block as measured by an EKG.

Phase II:

The primary outcome for Phase II(SA2) will be determining the efficacy of topical Verapamil HCl at the MTD for subjective symptoms of CRSwNP using the validated SNOT-22.

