4.2.2 SECONDARY ENDPOINTS

Phase Ib:

Intermediate toxicity will be defined as: a heart rate of <50, an asymptomatic BP reduction >30% from baseline or SBP <90mmHg, an asymptomatic AMP reduction >30% from baseline or MAP<55, an asymptomatic DBP reduction >30% from baseline, and a Meltzer Compliance Grade >4.

Mild toxicity will be defined as a Meltzer Compliance Grade of 2-3.

Phase II:

The secondary outcomes of Phase II will be to determine the efficacy of Verapamil HCl at the MTD as measured by a subjective 10cm visual analog scale(VAS), Meltzer topical irrigation satisfaction and compliance scores, and the validated Lund-Kennedy nasal endoscopy score(LKS).

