8 ASSESSMENT OF SAFETY

8.1 SPECIFICATION OF SAFETY PARAMETERS

Safety parameters that are also endpoints for Phase Ib are:

- a development of 2nd or 3rd degree heart block as measured by an EKG.
- a heart rate of <50
- an asymptomatic BP reduction >30% from baseline or SBP <90mmHg
- an asymptomatic AMP reduction >30% from baseline or MAP<55
- an asymptomatic DBP reduction >30% from baseline

All safety parameters will be recorded in a partcipants CRF at each study visit. All AEs will require reporting for the protection of human subjects.

If a heart block develops, treatment will be adjusted based on symptomatology. Completely asymptomatic patients can be observed. Patients with mild to moderate symptoms (hypotension, orthostasis, fatigue, dyspnea or angina) should be treated with 1liter NS bolus followed by Calcium Gluconate. Patients who are severely symptomatic and have failed the above interventions can also receive glucagon, norepinephrine, and finally pacing if necessary

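### Phase Ib: a symptomatic fall of more than 30% in BP, MAP or DBP that stays at or above SBP 90 and MAP 55, with no other qualifying sign, is neither DLT nor IT, although the same fall without symptoms is an IT

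*Combined protocol and SAP*

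**What the plan says.** Section 4.2.1 defines the DLT by heart block alone: "Dose Limiting Toxicity will be defined as a development of 2nd or 3rd degree heart block as measured by an EKG". The summary and 4.1 say the same.

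The IT definition in the summary and 4.2.2 begins "Intermediate toxicity will be defined as: a heart rate of <50, an asymptomatic BP reduction >30% from baseline or SBP <90mmHg" and ends, in 4.2.2, with "an asymptomatic DBP reduction >30% from baseline, and a Meltzer Compliance Grade >4". Section 4.1 has the same qualifier: "an asymptomatic MAP reduction >30% from baseline or MAP<55, an asymptomatic diastolic BP reduction >30% from baseline". Section 8.1 repeats it in the list of safety parameters: "an asymptomatic DBP reduction >30% from baseline". Mild toxicity (4.2.2) is a Meltzer grade only and does not cover blood pressure.

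These two classes drive the dose decisions. On escalation, 4.1 states: "Dose escalation will occur weekly in the absence of a single, any course, DLT or a second, any course, intermediate toxicity". The maximal administered dose (MAD) is the dose where "at least 2 DLTs or 4 ITs occur and the MTD will then be assigned to the immediate preceeding dose". Section 5.4.1 removes a Phase Ib participant for a DLT, more than one IT, or starting a contraindicated medicine. Section 2.3.1 names the hazard concerned: "Additional risks include bradycardia and hypotension".

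**The concern.** Because *asymptomatic* qualifies the relative falls, symptoms take an event out of the IT class, and nothing moves it up to DLT. No section gives a grade to a symptomatic fall. Section 8.1 mentions symptomatic hypotension only as treatment guidance once heart block has developed.

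The MTD is the Phase Ib primary endpoint and the dose for the 20 Phase II participants (4.1). A count that gives the worse form of a known drug effect less weight than the milder form errs toward too high a dose. A participant who withdraws because of such an event is replaced (4.1, 5.4.2), and the event still does not enter the count.

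**Working it through.** There is no stated figure to reproduce. The check applies the definitions to eligible blood pressures.

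**Inputs.** Baseline SBP at least 110 and DBP at least 70 (5.2). Relative limit 30%; floors SBP 90 and MAP 55; no DBP floor (4.1). MAP = (SBP + 2 × DBP)/3.

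**Reading taken.** Any one listed criterion makes an IT. The BP criterion is read as SBP. The SBP and MAP floors apply with or without symptoms, which is the narrower reading of the gap.

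**Step 1: which baselines leave room between the 30% limit and the floor?**
- SBP: 90/0.70 = 128.6. Only a baseline above 128.6 can fall by more than 30% and stay at or above 90.
- MAP: 55/0.70 = 78.6. The lowest eligible MAP is (110 + 140)/3 = 83.3, and 0.70 × 83.3 = 58.3, so every eligible participant has some room.
- DBP: no floor of its own, so there is room at every baseline as long as SBP and MAP stay above theirs.

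**Step 2: proportional falls.** If SBP and DBP fall by the same percentage, the largest fall that meets neither floor is min(1 − 90/SBP, 1 − 55/MAP).

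| Baseline | Largest fall above both floors | Window beyond 30% |
|---|---|---|
| 110/70 | 18.2% | none |
| 120/75 | 25.0% | none |
| 128/80 | 29.7% | none |
| 130/80 | 30.8% | 30–30.8% |
| 140/85 | 35.7% | 30–35.7% |
| 150/90 | 40.0% | 30–40.0% |
| 160/95 | 43.8% | 30–43.8% |

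**Step 3: examples** (HR at least 50, Meltzer grade 4 or lower, no heart block).
- 140/90 to 96/60: SBP −31.4%, DBP −33.3%, MAP 106.7 to 72.0 (−32.5%). IT without symptoms; unclassed with symptoms.
- 120/80 to 95/54 (discordant): SBP −20.8%, DBP −32.5%, MAP 93.3 to 67.7 (−27.5%). IT without symptoms; unclassed with symptoms.
- 120/80 to 82/54: an IT either way on the narrower reading, because SBP is below 90. If *asymptomatic* also governs the floors, the symptomatic case is unclassed too, so the gap is wider.

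**Step 4: the 20% halt in 8.5.** The protocol does not define the AE rate. Taking it as participants with an AE over participants enrolled:
- one affected: 1/5 = 20.0% reaches the limit; 1/6 = 16.7% does not;
- two affected: 2/10 = 20.0% reaches it; 2/11 = 18.2% does not.

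Removal follows a second IT, so if ITs accrue one at a time, no participant contributes more than two. Four ITs at a dose then need at least two affected participants.

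**The case against.** The strongest reply is that these events are neither ignored nor common, and that the halt acts before the MTD goes wrong.

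- **Other criteria may catch the event.** HR below 50 or a Meltzer grade above 4 makes it an IT, and heart block makes it a DLT. Section 2.3.1 lists bradycardia beside hypotension, so overlap is plausible. This stands and limits the point.
- **The window is narrow.** No proportional fall escapes at a baseline SBP of 110, 120 or 128, and nothing in the documents says discordant falls are expected. This stands.
- **The halt is mandatory.** The event is an AE (8.1.1), goes to the IRB and DSMB (8.4.1), and counts toward 8.5, which stops dosing and brings DSMB review. Section 5.5 also allows suspension for unacceptable risk, and the first dose at each step has an hour of hemodynamic monitoring (4.1). So a wrong MTD would usually also need the DSMB to let escalation continue. This stands, but none of these measures adds an IT or DLT to the MAD count. The two-participant argument also weakens above 10 enrolled, which is not ruled out: the summary's maximum of 40, less 20 for Phase II, leaves up to 20.
- **Exposure is low.** The top residual dose of 3.6 mg is 16.8/3.6 = 4.7 to 72.75/3.6 = 20.2 times below the intranasal equivalent of oral dosing in 2.1. This makes the event less likely. The margin rests on 3% retention, however: 3.6/0.03 = 120 mg goes into the bottle.
- **The authors may have meant symptomatic falls to rank above IT.** That is possible, but no section says so.

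A reader might infer that symptomatic hypotension goes unrecorded, or that any such event escapes the count. The documents support neither: AE reporting applies throughout, and on the narrower reading an SBP below 90 or MAP below 55 is an IT whatever the symptoms.

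**Conclusion.** The gap is real on the text and holds on either reading of the floors. The rule misclassifies a specific event in the count that sets the Phase Ib primary endpoint. It is a should-fix: the window is restricted, a mandatory halt with DSMB review stands behind it, and its frequency cannot be estimated from the documents.

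A reader might go further and infer that the MTD will come out a ladder step too high: a factor of 2.0 if the miss is at 0.6, 1.2 or 2.4 mg, 1.25 at 3.0 mg, or 1.2 at 3.6 mg. These are only the ratios between neighbouring doses in 6.1.7, conditional on a miscount having kept a dose below the MAD threshold. They are not an expected effect. A probability would need the rate of such falls and the share with symptoms, and the documents give neither.

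The conclusion rests on reading the IT list as any one criterion. The size of the backstop also assumes a per-participant AE rate. The escalation wording in 6.1.8 and 7.3.3 differs from 4.1, but that is a separate matter: each version turns on DLT and IT only, so the unclassed event holds back escalation under none of them.

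**What to change.** In the summary, 4.1, 4.2.2 and 8.1, delete *asymptomatic*, or write *symptomatic or asymptomatic*, so that every fall of more than 30% in BP, MAP or DBP counts as at least an IT. Both Step 3 examples that are now unclassed with symptoms then become ITs, and the doubt over whether the qualifier reaches the SBP and MAP floors goes away. The clinical team could choose to class symptomatic falls as DLT, but closing the gap does not require it.

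This is a wording-only amendment with no added visits, tests or planned participants. The downside is that escalation may stop slightly earlier, more so if symptomatic falls are made DLTs.
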